7.3.1 Unblinding at the Time of Disease Recurrence/Progression

As of 22-Sep-2021, enrollment for new participants was closed. **Per Protocol Amendment 01, the objectives of this study have been amended to safety only.** The study will be unblinded to facilitate ongoing safety monitoring.

If a participant is assessed by the Investigator to have HCC disease recurrence/progression ([Section 9.1.1](#) [Imaging Assessment for the Study]), and unblinding is considered necessary to inform the appropriate subsequent anti-cancer therapy, the study treatment assignment for the participant can be obtained by the Investigator through IRT for non-emergency unblinding. The Investigator should follow the procedures outlined in the IRT Manual to obtain the participant's study treatment assignment. The BMS central study team (including, but not limited to, clinical, statistics, and data management) will remain blinded to treatment assignment.

Investigators must wait for confirmation of recurrence/progression from the BICR prior to non-emergency unblinding for the purpose of initiating subsequent anti-cancer therapy, unless clinical considerations require immediate intervention (eg, symptomatic brain metastases). If subsequent anti-cancer therapy (including systemic cancer therapy, radiotherapy, or tumor-directed surgery) is planned prior to BICR confirmation of recurrence/progression, the Investigator must contact the BMS Medical Monitor or Clinical Scientist to discuss the case prior to the start of any of such therapy.

If a participant is diagnosed with a non-HCC secondary cancer, blinding should be preserved unless specific circumstances, to be discussed with the BMS Medical Monitor or Clinical Scientist, require that the blind be broken (eg, participant has metastases and could enroll on a clinical trial but would be ineligible if he or she had prior checkpoint inhibitor therapy).

For this study, the method of unblinding for emergency purposes is through the IRT. For information on how to unblind in an emergency, please see [Section 7.3](#) (Blinding).

7.4 Dosage Modification

7.4.1 Nivolumab and Ipilimumab Dose Modifications

No dose modifications for nivolumab or ipilimumab are allowed.

7.4.2 Nivolumab and Ipilimumab Dose Delay Criteria

Dose delay criteria summarized in [Table 7.4.2-1](#) apply for all drug-related AEs, regardless of whether the event is attributed to nivolumab or ipilimumab or both. Delay administration of both nivolumab and ipilimumab if any of the delay criteria in [Table 7.4.2-1](#) are met.

Delay nivolumab and ipilimumab for any AE, laboratory abnormality, or intercurrent illness which, in the judgment of the Investigator, warrants delaying the dose of study medication. Delay study therapy also in cases of confirmed or suspected SARS-CoV-2 infection.

Participants receiving nivolumab plus ipilimumab who have drug-related toxicities that meet the criteria for dose delay should have both drugs (nivolumab and ipilimumab) delayed until retreatment criteria are met, regardless of whether or not the event is attributed to 1 of the drugs. Tumor assessments for all participants should continue as per protocol even if dosing is delayed.

Participants who require delay of nivolumab and ipilimumab should be re-evaluated weekly, or more frequently if clinically indicated, and resume study treatment when re-treatment criteria are met (see [Section 8.1.3](#) [Post Study Treatment Study Follow-up]). Please see also [Appendix 6](#) (IO Management Algorithms) for guidance on appropriate management and follow-up of AEs.

[Table 7.4.2-1](#) summarizes criteria for delaying, resuming, and discontinuing dose of both nivolumab and ipilimumab.

Table 7.4.2-1: Adverse Event Criteria for Delay, Resume, and Discontinue of Nivolumab and Ipilimumab

Drug-Related Adverse Event (AE) per CTCAE V5	Severity	Action Taken	Clarifications, Exceptions, and Resume Criteria
Gastrointestinal			
Colitis or Diarrhea	Grade 2	Delay dose	Dosing may resume when AE resolves to baseline
	Grade 3	Permanently discontinue	
	Grade 4	Permanently discontinue	
Renal			
Serum Creatinine Increased	Grade 2 or 3	Delay dose	Dosing may resume when AE resolves to Grade \leq 1 or baseline value
	Grade 4	Permanently discontinue	
Pulmonary			
Pneumonitis	Grade 2	Delay dose	Dosing may resume after pneumonitis has resolved to \leq Grade 1.
	Grade 3 or 4	Permanently discontinue	
Hepatic			
Aspartate aminotransferase (AST), alanine aminotransferase (ALT), or total bilirubin (T.Bili) increased	
AST/ALT
 
 • If Baseline AST/ALT is within normal limits: 
 – AST or ALT $>$ 3\times upper limit of normal (ULN) • If Baseline AST/ALT $>$ ULN and up to 3\times ULN: 
 – AST or ALT $>$ 5\times ULN 	Delay dose	
 • Dosing may resume when AST or ALT values return to normal or \leq 3\times ULN • Exceptions: 
 – If baseline AST or ALT $>$ 3\times and \leq 5\times ULN, dosing may resume when AST or ALT values return to \leq 5\times ULN – Participants with AST or ALT meeting discontinuation criteria should have treatment permanently discontinued

Table 7.4.2-1: Adverse Event Criteria for Delay, Resume, and Discontinue of Nivolumab and Ipilimumab

Drug-Related Adverse Event (AE) per CTCAE V5	Severity	Action Taken	Clarifications, Exceptions, and Resume Criteria
	
 • If Baseline AST/ALT > 3× and ≤ 5× ULN: 
 – AST or ALT 2-fold increase OR AST or ALT of 8× ULN (whichever is lower) 		
	
Total Bilirubin
 
 • If Baseline T.Bili is within normal limits: 
 – T.Bili > 1.5× ULN • If Baseline T Bili > ULN and up to 1.5× ULN: 
 – T. Bili > 3× ULN • If Baseline T.Bili > 1.5× and ≤ 3× ULN: 
 – T.Bili 2-fold increase 	
Delay dose
	
 • Dosing may resume when laboratory values return to normal or ≤ 1.5× ULN • Exceptions: 
 – If baseline T.Bili > 1.5× and ≤ 3× ULN, dosing may resume when T.Bili values return to ≤ 3× ULN – Participants with T.Bili meeting discontinuation criteria should have treatment permanently discontinued
	
 • AST or ALT > 10× ULN for > 2 weeks • AST or ALT > 15× ULN irrespective of duration • T.Bili > 5× ULN for participants with normal T.Bili at entry OR > 8× ULN for participants with elevated T.Bili at study 	
Permanently discontinue
	

Table 7.4.2-1: Adverse Event Criteria for Delay, Resume, and Discontinue of Nivolumab and Ipilimumab

Drug-Related Adverse Event (AE) per CTCAE V5	Severity	Action Taken	Clarifications, Exceptions, and Resume Criteria
	entry, irrespective of duration • Potential drug-induced liver injury; Concurrent ALT > 10× ULN AND T.Bili ≥ 2× ULN or baseline value (if elevated bilirubin at study entry), and no other immediately apparent cause of hepatic lab abnormalities.		
Endocrinopathy			
Adrenal Insufficiency	Grade 2 adrenal insufficiency	Delay dose	Dosing may resume after adequately controlled with hormone replacement.
	Grade 3 or 4 adrenal insufficiency or adrenal crisis	Delay dose or permanently discontinue	Mandatory discussion with and approval from the BMS Medical Monitor/Clinical Scientist needed prior to resuming therapy. If adrenal insufficiency resolves or is adequately controlled with physiologic hormone replacement, participant may not require discontinuation of study drug.
Hyperglycemia	Hyperglycemia requiring initiation or change in daily management (Grade 2 or 3)	Delay dose	Dosing may resume if hyperglycemia resolves to Grade ≤ 1 or baseline value or is adequately controlled with glucose-controlling agents.
	Grade 4	Delay dose or permanently discontinue	Mandatory discussion with and approval from the BMS Medical Monitor/Clinical Scientist needed prior to resuming therapy. If hyperglycemia resolves, or is adequately controlled with glucose-controlling agents, participant may not require discontinuation of study drug.

Table 7.4.2-1: Adverse Event Criteria for Delay, Resume, and Discontinue of Nivolumab and Ipilimumab

Drug-Related Adverse Event (AE) per CTCAE V5	Severity	Action Taken	Clarifications, Exceptions, and Resume Criteria
Hypophysitis/Hypopituitarism	Symptomatic Grade 1-3 that is also associated with corresponding abnormal lab and/or pituitary scan	Delay dose	Dosing may resume if endocrinopathy resolves to be asymptomatic or is adequately controlled with only physiologic hormone replacement.
	Grade 4	Delay dose or permanently discontinue	Mandatory discussion with and approval from the BMS Medical Monitor/Clinical Scientist needed prior to resuming therapy. If endocrinopathy resolves or is adequately controlled with physiologic hormone replacement, participant may not require discontinuation of study drug.
Hyperthyroidism or Hypothyroidism	Grade 2 or 3	Delay dose	Dosing may resume if endocrinopathy resolves to be asymptomatic or is adequately controlled with only physiologic hormone replacement or other medical management.
	Grade 4	Delay dose or permanently discontinue	Mandatory discussion with and approval from the BMS Medical Monitor/Clinical Scientist needed prior to resuming therapy. If endocrinopathy resolves or is adequately controlled with physiologic hormone replacement or other medical management, participant may not require discontinuation of study drug.
Skin			
Rash	Grade 2 rash covering > 30% body surface area or Grade 3 rash	Delay dose	Dosing may resume when rash reduces to ≤ 10% body surface area
	Suspected Stevens-Johnson syndrome (SJS), toxic epidermal necrolysis (TEN) or drug reaction with eosinophilia and systemic symptoms (DRESS)	Delay dose	Dosing may resume if SJS, TEN, or DRESS is ruled out and rash reduces to is ≤ 10% body surface area

Table 7.4.2-1: Adverse Event Criteria for Delay, Resume, and Discontinue of Nivolumab and Ipilimumab

Drug-Related Adverse Event (AE) per CTCAE V5	Severity	Action Taken	Clarifications, Exceptions, and Resume Criteria
	Grade 4 rash or confirmed SJS, TEN, or DRESS	Permanently discontinue	
Neurological			
Guillain-Barre Syndrome (GBS)	Any Grade	Permanently discontinue	
Myasthenia Gravis (MG)	Any Grade	Permanently discontinue	
Encephalitis	Any Grade encephalitis	Delay dose	After workup for differential diagnosis, (ie, infection, tumor-related), if encephalitis is not drug related, then dosing may resume when AE resolves
	Any Grade drug-related encephalitis	Permanently discontinue	
Myelitis	Any Grade myelitis	Delay dose	After workup for differential diagnosis, (ie, infection, tumor-related), if myelitis is not drug related, then dosing may resume when AE resolves
	Any Grade drug-related myelitis	Permanently discontinue	
Neurological (other than GBS, MG, encephalitis, or myelitis)	Grade 2	Delay dose	Dosing may resume when AE resolves to baseline
	Grade 3 or 4	Permanently discontinue	
Myocarditis			
Myocarditis	Symptoms induced from mild to moderate activity or exertion	Delay dose	Dosing may resume after myocarditis has resolved
	Severe or life threatening, with symptoms at rest or with minimal activity or exertion, and/or where intervention indicated.	Permanently discontinue	

Table 7.4.2-1: Adverse Event Criteria for Delay, Resume, and Discontinue of Nivolumab and Ipilimumab

Drug-Related Adverse Event (AE) per CTCAE V5	Severity	Action Taken	Clarifications, Exceptions, and Resume Criteria
Other Clinical AE			
Pancreatitis:	Grade 3 with symptoms	Delay dose	Note: Grade 3 increased amylase or lipase without signs or symptoms of pancreatitis does not require dose delay.
			Dosing may resume when patient becomes asymptomatic.
Amylase or Lipase increased	Grade 4	Permanently discontinue	
Uveitis	Grade 2 uveitis	Delay dose	Dosing may resume if uveitis responds to topical therapy (eye drops) and after uveitis resolves to Grade \leq 1 or baseline. If patient requires oral steroids for uveitis, then permanently discontinue study drug.
	Grade 3 or 4 uveitis	Permanently discontinue	
Other Drug-Related AE (not listed above)	Grade 2 non-skin AE, except fatigue	Delay dose	Dosing may resume when AE resolves to Grade \leq 1 or baseline value.
	Grade 3 AE - First occurrence lasting \leq 7 days	Delay dose	Dosing may resume when AE resolves to Grade \leq 1 or baseline value.
	Grade 3 AE- First occurrence lasting $>$ 7 days	Permanently discontinue	
	Recurrence of Grade 3 AE of any duration	Permanently discontinue	
	Grade 4 or Life-threatening adverse reaction	Permanently discontinue	
Other Lab abnormalities			
Other Drug-Related lab abnormality (not listed above)	Grade 3	Delay dose	
Exceptions: No delay required for: Grade 3 lymphopenia
 
Permanent Discontinuation for: Grade 3 thrombocytopenia $>$ 7 days or associated with bleeding.

Table 7.4.2-1: Adverse Event Criteria for Delay, Resume, and Discontinue of Nivolumab and Ipilimumab

Drug-Related Adverse Event (AE) per CTCAE V5	Severity	Action Taken	Clarifications, Exceptions, and Resume Criteria
	Grade 4	Permanently discontinue	Exceptions: The following events do not require discontinuation of study drug: 
 • Grade 4 neutropenia ≤ 7 days • Grade 4 lymphopenia or leukopenia • Grade 4 isolated electrolyte imbalances/abnormalities that are not associated with clinical sequelae and are responding to supplementation/appropriate management within 72 hours of their onset
Infusion Reactions (manifested by fever, chills, rigors, headache, rash, pruritus, arthralgia, hypotension, hypertension, bronchospasm, or other allergic-like reactions.)			
Hypersensitivity reaction or infusion reaction	Grade 3 or 4	Permanently discontinue	Refer to Section 7.4.3 on Treatment of Related Infusion Reactions

Abbreviations: AE = adverse event; ALT = alanine aminotransferase; AST = aspartate aminotransferase; BMS = Bristol-Myers Squibb; CTCAE V5 = National Cancer Institute Common Terminology Criteria for Adverse Events version 5.0; DRESS = drug reaction with eosinophilia and systemic symptoms; GBS = Guillain-Barre syndrome; MG = myasthenia gravis; SJS = Stevens-Johnson syndrome; T.Bili = total bilirubin; TEN = toxic epidermal necrolysis; ULN = upper limit of normal.

7.4.3 Treatment of Nivolumab- or Ipilimumab-related Infusion Reactions

Since nivolumab and ipilimumab contains only human Ig protein sequences, it is unlikely to be immunogenic and induce infusion or hypersensitivity reactions. However, if such a reaction were to occur, it might manifest with fever, chills, rigors, headache, rash, pruritus, arthralgias, hypotension, hypertension, bronchospasm, or other allergic-like reactions. All Grade 3 or 4 infusion reactions should be reported within 24 hours to the BMS Medical Monitor or Clinical Scientist and reported as an SAE if it meets the criteria. Infusion reactions should be graded according to National Cancer Institute (NCI) Common Terminology Criteria for Adverse Events (CTCAE) version 5.0 guidelines.

Treatment recommendations are provided below based on NCI CTCAE version 5.0 grading definitions and may be modified based on local treatment standards and guidelines, as appropriate.

For Grade 1 symptoms (mild reaction; infusion interruption not indicated; intervention not indicated):

- Remain at bedside and monitor participant until recovery from symptoms. The following prophylactic premedications are recommended for future infusions: diphenhydramine 50 mg (or equivalent) and/or acetaminophen/paracetamol 325 to 1000 mg at least 30 minutes before additional study treatment administrations.

For Grade 2 symptoms (therapy or infusion interruption indicated but responds promptly to symptomatic treatment (eg, antihistamines, non-steroidal anti-inflammatory drugs, narcotics, IV fluids); prophylactic medications indicated for ≤ 24 hours):

- Stop the study treatment infusion, begin an IV infusion of normal saline, and treat the participant with diphenhydramine 50 mg IV (or equivalent) and/or acetaminophen/paracetamol 325 to 1000 mg; remain at bedside and monitor participant until resolution of symptoms. Corticosteroid and/or bronchodilator therapy may also be administered as appropriate. If the infusion is interrupted, then restart the infusion at 50% of the original infusion rate when symptoms resolve; if no further complications ensue after 30 minutes, the rate may be increased to 100% of the original infusion rate. Monitor participant closely. If symptoms recur, then no further study medication will be administered at that visit.
- For future infusions, the following prophylactic premedications are recommended: diphenhydramine 50 mg (or equivalent) and/or acetaminophen/paracetamol 325 to 1000 mg should be administered at least 30 minutes before study treatment infusions. If necessary, corticosteroids (up to 25 mg of hydrocortisone or equivalent) may be used.

For Grade 3 or 4 symptoms (severe reaction, Grade 3: prolonged [eg, not rapidly responsive to symptomatic medication and/or brief interruption of infusion]; recurrence of symptoms following initial improvement; hospitalization indicated for other clinical sequelae [eg, renal impairment, pulmonary infiltrates]. Grade 4: Life threatening consequences; urgent intervention indicated).

- Immediately discontinue infusion of study treatment. Begin an IV infusion of normal saline and treat the participant as follows: Recommend bronchodilators, epinephrine 0.2 to 1 mg of a 1:1000 solution for subcutaneous administration or 0.1 to 0.25 mg of a 1:10,000 solution injected slowly for IV administration, and/or diphenhydramine 50 mg IV with methylprednisolone 100 mg IV (or equivalent), as needed. Participant should be monitored until the Investigator is comfortable that the symptoms will not recur. Study treatment will be permanently discontinued. Investigators should follow their institutional guidelines for the treatment of anaphylaxis. Remain at bedside and monitor participant until recovery of the symptoms.

In case of late-occurring hypersensitivity symptoms (eg, appearance of a localized or generalized pruritus within 1 week after treatment), symptomatic treatment may be given (eg, oral antihistamine or corticosteroids).

7.5 Preparation/Handling/Storage/Accountability

The IP should be stored in a secure area according to local regulations. It is the responsibility of the Investigator to ensure that IP is only dispensed to study Participants. The IP must be dispensed only from official study sites by authorized personnel according to local regulations.

The product storage manager should ensure that the study treatment is stored in accordance with the environmental conditions (temperature, light, and humidity) as determined by BMS. If concerns regarding the quality or appearance of the study treatment arise, the study treatment should not be dispensed and contact BMS immediately.

Study treatment not supplied by BMS will be stored in accordance with the package insert.

IP documentation (whether supplied by BMS or not) must be maintained that includes all processes required to ensure drug is accurately administered. This includes documentation of drug storage, administration and, as applicable, storage temperatures, reconstitution, and use of required processes (eg, required diluents, administration sets).

Further guidance and information for final disposition of unused study treatment are provided in [Appendix 2](#) and the CA20974W Pharmacy Manual.

7.5.1 Retained Samples for Bioavailability / Bioequivalence / Biocomparability

Not applicable.

7.6 Treatment Compliance

Study treatment will be administered in the clinical facility. Treatment compliance will be monitored by drug accountability as well as the participant's medical record and eCRF.

7.7 Concomitant Therapy

Prohibited and/or restricted treatments are outlined below.

7.7.1 Prohibited and/or Restricted Treatments

The following medications are prohibited during the study (unless utilized to treat drug-related AEs):

- Any live/attenuated vaccine (eg, varicella, zoster, yellow fever, rotavirus, oral polio, and measles, mumps, rubella [MMR]), within 30 days prior to randomization, during treatment, and until 100 days after the last dose.
- Immunosuppressive agents.
- Immunosuppressive doses of systemic corticosteroids (except as stated in [Section 6.2](#) [Exclusion Criteria] criterion 1) subcriterion 1) and [Section 7.7.3](#) [Permitted Therapy]).
- Any concurrent anti-neoplastic therapy (ie, chemotherapy, molecular targeted therapy, locoregional therapy, hormonal therapy, immunotherapy, palliative or non-palliative radiation therapy, or standard or investigational agents for treatment of HCC). TACE on demand is allowed as per protocol-defined criteria.
- Any botanical preparation (eg, herbal supplements or traditional Chinese medicines) intended to treat the disease under study or provide supportive care. Use of marijuana and its derivatives for treatment of symptoms related to cancer or cancer treatment are permitted if obtained by medical prescription or if its use (even without a medical prescription) has been legalized locally.
- Concurrent use of antiviral therapy containing interferon (IFN).

7.7.2 Other Restrictions and Precautions

- Participants with a condition requiring systemic treatment with either corticosteroids (> 10 mg daily prednisone equivalent) or other immunosuppressive medications within 14 days of randomization are excluded. Inhaled or topical steroids, and adrenal replacement steroid doses > 10 mg daily prednisone equivalent, are permitted in the absence of active autoimmune disease.
- Investigators are strongly encouraged to wait for confirmation of recurrence/progression from the BICR prior to initiating subsequent systemic cancer therapy, loco-regional therapy, or tumor-directed surgery for suspected recurrence/progression unless clinical considerations require immediate intervention (eg, symptomatic brain metastases). If subsequent systemic cancer therapy, loco-regional therapy, or tumor-directed surgery is planned prior to BICR confirmation of recurrence/progression, the Investigator must contact the BMS Medical Monitor or Clinical Scientist to discuss the case prior to the start of any of these procedures.

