5.4.10 Rationale for Unblinding

[REDACTED] Therefore, a decision was made by BMS in September 2021 to stop the study.

Upon implementation of Protocol Amendment 01, participants will be unblinded to allow BMS to continue safety monitoring the remaining participants on study without blinding while streamlining other study procedures. All investigators, ethics committees, and health authorities have been informed.

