9.1.1.4 BICR Determination of Progression or Recurrence

Not applicable per Protocol Amendment 01. Tumor assessments will be conducted by the investigator per local standard of care. The following information refers to the original study design.

Sites should submit all scans to the central imaging vendor on a rolling basis, throughout the duration of the study. BICR of scans will occur on a rolling basis, blinded to treatment arm, clinical data, and Investigator assessment of submitted scans. The BICR will be completed and the results (TTTP reached or not) provided to the site, as specified in the imaging vendor documents, provided there are no pending imaging queries to the site. All details on the timelines and associated process requirements will be outlined in the Imaging Manual.

Participants whose progression by TTTP criteria is not determined by the BICR will be required to continue tumor assessments (if clinically feasible) according to the protocol-specified schedule, or sooner if clinically indicated. Also, if participants discontinue treatment without radiographic progression (TTTP as assessed by BICR), tumor assessments will continue according to the protocol-specified schedule, as noted in [Section 2](#) (Schedule of Activities), until progression (TTTP as assessed by BICR), has been confirmed by BICR.

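### Do the leftover BICR references in Sections 7.3.1 and 7.7.2 hold up unblinding or next-line therapy now that Amendment 01 has ended central review?

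*Combined protocol and SAP*

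**What the plan says.** The Synopsis, Section 5.1.5.2 and Section 9.1.1.4 all mark BICR as no longer applicable. Section 9.1.1.4 puts it this way: "Not applicable per Protocol Amendment 01. Tumor assessments will be conducted by the investigator per local standard of care".

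Two sections still refer to a BICR read, and those sentences do not carry the label.

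- Section 7.7.2 states: "Investigators are strongly encouraged to wait for confirmation of recurrence/progression from the BICR prior to initiating subsequent systemic cancer therapy". The same bullet covers loco-regional therapy and tumor-directed surgery. It exempts cases needing urgent intervention. Where treatment is planned before BICR confirmation, it adds that "the Investigator must contact the BMS Medical Monitor or Clinical Scientist to discuss the case prior to the start of any of these procedures".
- Section 7.3.1 opens with text from the amendment: "The study will be unblinded to facilitate ongoing safety monitoring". Further down it keeps "Investigators must wait for confirmation of recurrence/progression from the BICR prior to non-emergency unblinding for the purpose of initiating subsequent anti-cancer therapy", with the same urgent-need exemption and the same sponsor contact. It also says that the sponsor's central study team "will remain blinded to treatment assignment".

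Section 5.4.10 explains why the blind is lifted: on implementation of the amendment, "participants will be unblinded to allow BMS to continue safety monitoring the remaining participants on study without blinding". Section 3.1.2 and the amendment's overall rationale both say that the amendment's changes take precedence wherever older requirements appear to conflict with them.

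**The concern.** Elsewhere the sponsor withdrew BICR text section by section with an explicit label, so unlabelled text looks as if it were meant to stay in force. On that reading a participant who progresses waits for a central read that nobody will perform, or else every case goes through the sponsor contact intended for exceptions. The two sections also seem to differ in force, one saying that investigators must wait and the other only encouraging it. A sentence that keeps the sponsor's team blinded appears to defeat the stated purpose of unblinding. At stake would be a delay to the next treatment after progression, and doubt over whether the people monitoring safety may see treatment assignment.

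**Working it through.** There is no figure to reproduce. The check sets the sections beside one another and asks what a site would actually be bound to do.

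1. **Timing.** Section 3.1.2 says the amendment's changes take effect when it is implemented at the site. Section 5.4.10 ties unblinding to that same event. Withdrawal of BICR and lifting of the blind therefore arrive together.

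2. **Starting therapy (Section 7.7.2).** The verb is one of encouragement. Urgent need is exempt. For treatment planned ahead of BICR confirmation the section asks for a discussion with the sponsor. It does not ask for approval, and it bars no treatment. Without a BICR read, every planned therapy falls into the discussion branch, so the most that happens is that a step written for exceptions becomes general.

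3. **Unblinding (Section 7.3.1).** The mandatory wait applies to an investigator obtaining one participant's assignment through IRT for a non-emergency reason. Once all remaining participants are unblinded, there is no such request left to delay.

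4. **Must against encouraged.** The sentences govern different acts: breaking a code in Section 7.3.1 and starting therapy in Section 7.7.2. On therapy planned before confirmation, both sections give the same contact route. They do not contradict each other.

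5. **The blinded team.** That sentence closes a paragraph about an individual code-break at progression. The position after study-wide unblinding is stated in Section 5.4.10, in Section 5.1.5.1 (the sponsor continues safety monitoring once participants are unblinded) and in Section 7.3 (unblinding serves ongoing safety monitoring). These agree, and they answer whether the monitoring team may see assignments.

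6. **Precedence.** Ending BICR is a change made by Amendment 01. A leftover instruction to wait for BICR is an apparent discrepancy with that change, and Section 3.1.2 resolves it in the amendment's favor. Section 8.1 already bases stopping of study treatment on progression as judged by the investigator, with treatment beyond progression as the exception.

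7. **Reach into the analysis.** Section 4 leaves one objective, safety and tolerability in treated participants. Section 10 plans only safety analyses, and Section 10.3.1 rules out formal efficacy analyses. Table 2-3 no longer calls for review of subsequent cancer therapy. Section 9.2.2 runs the minimum 100-day adverse-event window from the end of dosing, so the date on which later therapy begins does not move it. Section 5.2 gives 26 participants randomized, with enrollment closed. That is an upper bound on those affected, since only participants who progress after implementation could meet the wording.

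**The case for a change.** The strongest opposing point is the contact step. Both sections say the investigator must make contact before therapy that precedes BICR confirmation. Amendment 01 announces no change to that duty, so the precedence clause removes the wait more clearly than it removes the contact. Section 9 allows no waivers and requires adherence, so a site that skips the contact cannot tell from the text whether it has deviated. A general clause also leaves each site to decide which unlabelled sentences are dead, and the sponsor chose explicit labels in other sections.

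Part of this stands. The protocol does not say whether the contact continues now that no BICR read takes place. But the duty is to discuss a case with the medical monitor or clinical scientist, the same people a site would ask if in doubt. It neither prevents treatment nor changes what is collected for the safety tables. The worst outcome is an unnecessary call or an arguable minor deviation.

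**Conclusion.** The inconsistency is real but clerical: incomplete labelling in an amendment that closes the study down. No therapy is blocked, the unblinding rule has nothing left to act on, and the sponsor's access to assignments is settled elsewhere. The effect on any planned estimate, interval or error rate is nil, and the number of participants who could meet the wording is at most 26.

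This rests on two assumptions: that sites apply the precedence clause in Section 3.1.2, and that unblinding follows implementation promptly, as Section 5.4.10 describes. As a matter of document upkeep, Sections 7.3.1 and 7.7.2 must be reconciled with Sections 3.1.2, 5.1.5.2, 5.4.10 and 9.1.1.4 when the text is next reissued, and whether the contact step continues is for the sponsor to state. No view is taken here on the clinical criterion for later therapy. None of this calls for a change to the design or the analysis.
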